### ***12.1 Adverse events***

All adverse events occurring during the study period, i.e. from informed consent to the final telephone call, irrespective of a relation with the study drug/device/procedure of IUC insertion.

Concurrent diseases that are reported at the time of inclusion will not be considered as adverse events, however any changes in symptoms or severity will be reported as an adverse event.

## **Definitions**

### **12.1.1 Adverse Events**

Any untoward medical occurrence in a study participant administered an investigational medicinal product and which does not necessarily have a causal relationship with this treatment. An adverse event can therefore be any unfavorable and unintended sign, symptom or disease temporally associated with the use of an investigational, medicinal product whether or not considered related to the investigational medicinal product.

### **Adverse Device Event**

This includes any adverse event resulting from insufficiencies or inadequacies in the instructions for use, the deployment or insertion of the investigational medical device.

This includes any event that is a result of a use error or intentional abnormal use of the investigational medical device.

#### **12.1.2 Serious Adverse Events (SAE)**

An untoward medical occurrence or effect that results in:

- Death
- Life threatening condition
- Requires hospital stay or lead to a prolonged hospital stay
- Results in permanent or serious disability
- Fetal malformation
- Any other serious medical event according to the investigators judgement

#### **12.1.2 Serious Adverse Device Effect (SADE)**

Adverse device effect that has resulted in any of the consequences characteristic of a serious adverse event.

#### **12.1.4 Suspected Unexpected Serious Adverse Reaction (SUSAR)**

A suspected unexpected serious adverse reaction of a study drug resulting in any condition mentioned above (12.1.1).

## ***12.2 Assessment of Adverse Event***

### **12.2.1 Assessment of severity**

An adverse event will be graded as:

- Mild = the subject is aware of the event but the event is easily tolerated
- Moderate = the subject experiences sufficient discomfort and the symptoms affect daily activities
- Severe = the subject experience significant impairment of functioning and the symptoms substantially affect daily activities

Note: a distinction should be drawn between serious and severe AEs. The term severe is used to describe the intensity of the event and the event does not necessarily need to be considered defining regulatory reporting obligations.

### **12.2.2 Assessment of causality**

The following definitions will be used to estimate the relation with adverse event and the study drug:

- Probable = clinically/biologically highly plausible and there is a plausible time sequence between the onset of the AE and the administration of the study drug. There is sufficient documentation to suspect a casual relationship
- Possible = clinically/biologically plausible and the relation cannot be rejected
- Unlikely = a causal relation is improbable and other explanation is more likely
- Not possible to evaluate = any relationship cannot be ruled out
- For medical device reporting two additional levels: “not related” (causal relationship can definitely be ruled out) and “causal relationship established” (when causal relationship can be established beyond reasonable doubt) will be used.
- The sponsor and the investigators will for medical devices distinguish between the serious adverse events related to the investigational device and those related to the procedures (any procedure specific to the clinical investigation). An adverse event can be related both to procedures and the investigational device. Complications of procedures are considered not related if the said procedures would have been applied to the patients also in the absence of investigational device use/application.

### ***12.3 Reporting of AE, SAE and SUSARs***

- All patients will be asked for adverse events at every visit/contact with the investigator or study nurse/midwife with the exception for what is mentioned under 13.1
- Adverse events will be reported irrespective if the event has any relation with the study drug or not
- All Adverse events must be recorded in the CRF, defining the relationship to study medication, severity and seriousness. Adverse Events should also be recorded in the patient records if applicable
- If a reported SAE is present when the patient completes the study the event must be followed for up to three months past the final visit or followed until final outcome is known or the condition is stable

- AE/SAE will be registered until the end of the study

### **12.3.1 Reporting of SAE, SADE and USADE**

- any SAE and any Device Deficiency that might have led to a SAE if: a) suitable action had not been taken or b) intervention had not been made or c) if circumstances had been less fortunate and in addition new findings/updates in relation to already reported events must be reported to the sponsor on a separate SAE report form within 24 hours of the initial notification of the event- for device deficiencies regulatory requirement is within 3 days- however, a 24 hour period will be maintained for all serious adverse events in this trial.
- The initial notification to the sponsor can be made on a SAE-report form, by e-mail or telephone
- At the time of initial reporting the investigator must provide a minimum requirement, the patient number, birth date, description of the SAE and a preliminary assessment of causality
- Supplemental information shall be reported by the investigator to the sponsor as soon as possible. If the SAE is fatal or life-threatening the investigator is responsible to report follow-up information to the sponsor within 5 days after the initial report
- Reportable medical device events must be reported by the sponsor at the same time to all the National Competent Authorities where the clinical investigation has commenced. This includes
  - for all reportable events as described above which indicate an imminent risk of death, serious injury, or serious illness and that requires prompt remedial action for other patients/subjects, users or other persons or a new finding to it: immediately, but not later than 2 calendar days after awareness by sponsor of a new reportable event or of new information in relation with an already reported event.
  - any other reportable events as described above or a new finding/update to it: immediately, but not later than 7 calendar days following the date of awareness by the sponsor of the new reportable event or of new information in relation with an already reported event.

### **12.3.2 Reporting SUSAR**

**Sponsor is obliged to report:**

- Any suspected serious unexpected reaction of the study drug (SUSAR) which is life threatening or fatal to the Medical Products Agency MPA ("Läkemedelsverket, LMV") as soon as possible and not later than 7 days after the responsible investigator has been aware of the event. The report should be sent to MPA and the Regional Ethical Review Board (RERB). Relevant follow-up information of the report should be sent within additional 8 days (maximum of 15 days from initial report)
- A suspected serious unexpected reaction of the study drug/device (SUSAR) that is **not** life threatening or fatal should be reported as soon as possible but within a maximum of 15 days to the MPA and the RERB
- All SUSARs should be reported to the MPA on a CIOMS-form and with assistance of the MPA also reported into the Eudra Vigilance Clinical Trial Module

During the study, the sponsor should report all SAEs with a suspected relation to the study drug, and SUSAR, to the MPA and RERB once a year. Moreover, a safety report concerning the patients included in the study should be supplied together with a summary on a risk/benefit evaluation for the patients participating in the study. The sponsor is obliged to inform all investigators about occurring SUSARs during the study period.

#### ***12.4 Serious breaches and urgent safety actions***

A serious breach means a breach likely to affect to a significant degree the safety and rights of a subject or the reliability and robustness of the data generated in the study protocol.

##### In case of serious breaches:

The sponsor should immediately notify the MPA and RERB about a serious breach of this protocol. An initial report can be done by telephone but must be followed by a written report

- The sponsor and the investigators will when necessary immediately take action to protect the patients from immediate danger
- All patients will be taken care of in the health care system
- The use of the investigational drug will be immediately stopped
- The sponsor may consider stopping the trial temporarily or institute complementary supervision
- In case of a serious event that may cause urgent safety actions the sponsor should be

informed as soon as possible. Moreover, the MPA and the RERB should be informed by the sponsor as soon as possible and the safety actions taken should be specified. The initial report may be oral or written but shall be followed by a written report concerning the new circumstances and taken and planned actions

- The report to the MPA should be done using the EU-common form for substantial amendments

### ***12.5 Safety analysis***

An interim analysis of results will be performed when 50 percent of women have been recruited in any gestational strata. If expulsion rates exceed 20 percent or if acceptability rates are below 50 percent by the 3 month follow up the study will be stopped. If the study is prematurely interrupted or stopped due to any reason this will be reported to the Medical Products Agency. When the study is completed according to plan this will also be reported to the Medical Products Agency

## **13 Data collection and data handling**

Every participant will be given an individual, study specific number (i.e study identifying code) at the time of inclusion. A code key with each individual personal data connected to the identifying code will be created (i.e patient identification log) and stored at each center in a way that only authorized persons have access.

All data will be collected in an electronic CRF with the identifying code. The data CRF will thus be transferred in original to the sponsor and stored electronically according to the data protection act. Each study site will hold a printed paper copy of the CRF which will be kept in a locked facility.

Statistical analyses will be performed using SPSS statistical software. All reports will be on group level and none of the study subjects will be identifiable.

## **15 Procedure for informed consent**

Women will receive written and oral information about the study at the first visit at the family

planning unit from the attending physician according to the principles of the Helsinki Declaration. They will have an opportunity to ask questions. If the woman chooses IUC as post abortion contraception, agrees to participate and is deemed eligible she will sign informed consent in the presence of the attending physician at that consultation or at any time prior to the abortion. This procedure will not differ between study sites. Informed consent and participation in the study will be noted in the electronic patient records along with the individual study subject number and the allocation (immediate or delayed insertion). The Swedish national guidelines on medical abortion will be followed by all sites ([www.sfog.se](http://www.sfog.se)).

All centers will have a specific, GCP-certified study nurse-midwife who will act as the study coordinator and collect the individual informed consent forms which will be kept in a locked facility. Participating women will receive a specific appointment for insertion of the IUC according to the wishes of the woman and the pre-defined allocation window. At the time of insertion participation will be re-confirmed by the inserter.

## **16 Regulatory requirements**

The study will be conducted in adherence to the approved study protocol and the latest version of the Declaration of Helsinki, ICH-GCP E6 addendum and all relevant laws and regulations.

### ***16.1 Applications, and substantial amendments***

The study has received RERB approval at Karolinska Institutet with number 2016/1685-31/1. However, due to ongoing applications and lack of funding the study has not been able to start until now when sufficient funding has been ensured. A current modification of the exact immediate timing of insertion in conjunction with this application has been approved with number 2018-48/32.

If substantial changes in the protocol or patient information or consent will be undertaken, an applications will be sent to the MPA using the "Substantial amendment notification form" as well as the RERB. The study will not start until all approvals by the MPA and RERB are in order.

Changes in the protocol that might affect the safety, physical or psychological integrity, change the scientific value of the study or may be considered as important of any other reason

should be considered as substantial changes. If the study has been temporarily stopped and then re-started, this should also be considered as a substantial change. The study will be performed according to the protocol. All protocol deviations will be noted and kept in a protocol deviation log describing the deviation and actions undertaken. All protocol deviations will be monitored by the PI and the appointed monitor and classified as minor, major or severe. All severe protocol deviations will be reported to the RERB and the MPA.

## **17 Statistical considerations - Sample size**

### ***17.1 Justification of power calculation***

A total of 720 women will be recruited. In order to be able to show a difference of 80 percent in IUC usage in the immediate insertion group at 6 months post insertion compared to 60 percent use in the delayed group with a power of 90 percent and an alpha of 0.05 we would need to randomize 109 women in each group. If close to 100 percent of women receive the IUC in the immediate group and there is an expulsion rate of maximum 15 percent (immediate post placental insertion after delivery has expulsion rates of 15 percent) and some women have the IUC removed a use of approximately 80 percent could be expected in the immediate group. In the delayed group fewer women are estimated to come for insertion and the expulsion rate is estimated at 5 percent.

We will stratify women in three gestational age categories ( $\leq 9$  weeks+0 days, 9weeks +1 day  $\leq 12$  weeks+0 days, and  $>12$  weeks) to make study data more internationally applicable. We will compensate for surgical procedures due to incomplete abortions and prolonged bleeding which is estimated to be needed in approximately 3-5 percent (13). We will also compensate for a 15 percent loss to follow up which is commonly seen in studies in abortion. Thus, we will randomize 240 women in each gestational strata (total 720 women). Analysis will be presented as intention to treat for all randomized women as well as per protocol for women completing the 6 month follow up (see analysis plan). Follow up at 3, 6 and 12 months will be performed by telephone/email. In women who does not attend FU electronic patient records will be searched for main and secondary outcomes (safety, pregnancy, abortion).

- Primary outcome:

The primary outcome is the difference in women with IUC use at 6 months between the two groups (immediate and delayed insertion). The results will be analyzed by Fisher's exact test. A sensitivity analysis will be performed using logistic regression taking center, parity and age into account.

- Analysis populations

The main analysis population for primary outcome will be a modified intention to treat (mITT). This population is all randomized women, with medical abortion, and follow up for main outcome recorded at 6 months. Hence, also women with no insertion and women experiencing expulsion are included in this mITT.

A sensitivity analysis will be performed on a strict ITT-population consisting of all randomized women having had medical abortion. In this analysis it is required to impute the outcome for women lost to follow up.

- Secondary efficacy outcomes:

1. Abortion rate as difference in proportion of individuals in each group at 3, 6 and 12 months,

Since both the primary outcome and this outcome involve data from different time-points several tests can be performed. In order to reduce the risk for type-I error each research question will be addressed with a global test including all available time-points first, before studying individual time-points. The data has a repeated-measure structure with a dichotomous outcome and most likely more observations available for early time-point compared to later time-points. To properly handle this data-structure we will use a multivariate permutation test based on a Fisher's combination function of individual  $p$ -values from time-specific tests (Fisher's exact test). If this global test is non-significant no individual time-points will be considered significant

2. Difference in the proportion of women who successfully have the IUC inserted (success versus failure),

Analyzed by Fisher's exact test.

- Secondary safety outcomes

1. rate of complications such as expulsions, perforations, infections. (Fisher's exact test)
2. Length of post abortion bleeding (difference in mean number of days in groups and per IUC use (hormonal/copper). Analyzed by T-test or Mann-Whitney U-test depending on the observed distribution (normal or skewed).
3. Pain at insertion on a VAS. Analyzed by Student's t-test

These secondary analyses concern safety where it is not sensible to adjust for multiple testing. The adjustments (with e.g. Bonferroni) increases the risk for type-II errors. As safety issues are very important we do not wish to increase the risk for type-II errors. Moreover, the analyses are listed under secondary endpoints so this implies that the results should be interpreted with more caution compared to the primary result.

- Secondary acceptability outcomes
  1. preferred method: immediate or delayed and if they would recommend their timing of insertion to a friend (yes/no). Analyzed by multivariate logistic regression with group, demographic variables and type of IUC (hormonal/copper) as explanatory variables.

Secondary analyses will be performed on all women with available data.

- Interim analysis:

In the interim analysis no analyses of efficacy will be performed. Hence there is no need to adjust any statistical test due to the interim analysis.

All test will be performed at the 5% significance level. The analysis plan has been developed by the principal investigator and [name], adjunct professor in medical statistics, Statisticon AB.

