**Sample size and calculated power**

*Justification of power calculation*

A total of 720 women will be recruited. In order to be able to show a difference of 80 percent in IUC usage in the immediate insertion group at 6 months post insertion compared to 60 percent use in the delayed group with a power of 90 percent and an alpha of 0.05 we would need to randomize 109 women in each group.

If close to 100 percent of women receive the IUC in the immediate group and there is an expulsion rate of maximum 15 percent (immediate post placental insertion after delivery has expulsion rates of 15 percent) and some women have the IUC removed a use of approximately 80 percent could be expected in the immediate group. In the delayed group fewer women are estimated to come for insertion and the expulsion rate is estimated at 5 percent.

We will stratify women in three gestational age categories ( $\leq 9$  weeks+0 days, 9weeks +1 day  $\leq 12$  weeks+0 days, and  $>12$  weeks) to make study data more internationally applicable. We will compensate for surgical procedures due to incomplete abortions and prolonged bleeding which is estimated to be needed in approximately 3-5 percent (13). We will also compensate for a 15 percent loss to follow up which is commonly seen in studies in abortion. Thus, we will randomize 240 women in each gestational strata (total 720 women). Analysis will be presented as intention to treat for all randomized women as well as per protocol for women completing the 6 month follow up (see analysis plan). Follow up at 3, 6 and 12 months will be performed by telephone/email. In women who do not attend FU electronic patient records will be searched for main and secondary outcomes (safety, pregnancy, abortion).

Women will be recruited at several sites in Sweden. Recruitment (numbers) is not expected to be equal at each site but this will be considered in the statistical analysis.

Statistical advice from statistician [name] (adjunct professor and professional medical statistician) has been sought for study design, power calculation, and analysis plan.

Randomization:

The randomization ratio between intervention and control group will be 1:1 in permuted blocks of 4-8 in three strata and per site.

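### 240 women per gestational stratum does not cover the 15% loss to follow-up that the protocol says it compensates for; power within a stratum is about 85%, not 90%

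*Protocol*

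**What the plan says.** Protocol section 17.1 assumes "a difference of 80 percent in IUC usage in the immediate insertion group at 6 months post insertion" and "compared to 60 percent use in the delayed group". From this it states that "with a power of 90 percent and an alpha of 0.05 we would need to randomize 109 women in each group".

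It then names two allowances. The first is "We will compensate for surgical procedures due to incomplete abortions and prolonged bleeding which is estimated to be needed in approximately 3-5 percent". The second is "We will also compensate for a 15 percent loss to follow up which is commonly seen in studies in abortion". The conclusion follows directly: "Thus, we will randomize 240 women in each gestational strata (total 720 women"). The same derivation appears in section 5 under *Sample size and calculated power*, where the allocation is also given: "The randomization ratio between intervention and control group will be 1:1".

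Three other statements bear on the point:

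- Section 17.1 names Fisher's exact test for the primary outcome, and "All test will be performed at the 5% significance level".
- The main analysis population in section 17.1 is a modified intention-to-treat (mITT) set: women who were randomised, had a medical abortion and have a 6-month outcome on record. Imputation is foreseen only for the strict ITT sensitivity analysis.
- Section 5, *Variables and measures*, says the primary outcome is evaluated as a proportion within each gestational stratum.

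**The concern.** The requirement of 109 per group, the claimed allowance for losses and the total of 240 per stratum cannot all hold. Going from 218 to 240 adds about 10%, which is less than the 15% loss to follow-up by itself. Women without a 6-month outcome leave the main analysis set, so the uncovered loss reduces the number analysed.

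A separate and smaller point adds to it: 109 comes from a chi-square formula, while the named test is Fisher's exact test, which needs more women for the same power.

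What is at stake is how a single stratum is read. The protocol justifies the strata by the wish to make results applicable in countries that use medical abortion only at certain gestations, so stratum results will be looked at. A non-significant stratum could be taken as a negative result at 90% power when the plan's own assumptions give less.

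**Working it through.** **Inputs.** From sections 5 and 17.1: 80% and 60% use; power 90%; alpha 0.05 (sidedness not stated; two-sided reproduces the plan's figure); 1:1 allocation; 15% loss to follow-up; 3-5% surgical procedures; 240 per stratum, so 120 per arm.

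**1. Reproducing 109.** Two-sided chi-square formula with pooled variance and no continuity correction:

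n = [1.96 x sqrt(2 x 0.7 x 0.3) + 1.2816 x sqrt(0.8 x 0.2 + 0.6 x 0.4)]² / 0.2² = 108.2, rounded up to 109.

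The plan's figure is matched. Variants do not match it: 119 with continuity correction, 106 with unpooled variance, 108 with the arcsine formula, 89 one-sided.

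**2. What 240 covers.** 1 - 109/120 = 9.2%.

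**3. What the stated losses need.**

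| Allowance | Per arm | Per stratum |
|---|---|---|
| 15% loss only | 109/0.85 = 128.2, so 129 | 218/0.85 = 256.5, so 257 |
| 15% loss and 3% surgical | 109/(0.85 x 0.97) = 132.2, so 133 | 265 |
| 15% loss and 5% surgical | 109/(0.85 x 0.95) = 135.0, so 135 | 270 |

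The weaker rule of multiplying by 1.15 still gives 218 x 1.15 = 250.7, so 251 per stratum. Neither rule gives 240.

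**4. Evaluable women per arm and stratum out of 120.** 120 x 0.85 = 102. If 3% or 5% surgical cases are also lost: 120 x 0.85 x 0.97 = 98.9, or 120 x 0.85 x 0.95 = 96.9.

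**5. Power for 80% versus 60%, two-sided 5%.** Fisher's test by full enumeration of both binomial distributions; chi-square by the formula in step 1 solved for power.

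| Evaluable per arm | Fisher's exact | Uncorrected chi-square |
|---|---|---|
| 97 (15% and 5% lost) | 83.4% | 86.6% |
| 99 (15% and 3% lost) | 84.2% | 87.2% |
| 102 (15% lost) | 85.4% | 88.2% |
| 109 (plan's requirement) | 87.6% | 90.2% |
| 120 (no loss) | 90.8% | 92.7% |

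Fisher's test first reaches 90% at 117 per arm (90.1%). So 120 per arm gives 90% with this test only if almost nobody is lost.

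**6. Pooled over the three strata.** 3 x 102 = 306 per arm gives 99.97% with Fisher's test; 3 x 97 = 291 gives 99.95%.

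**The case against.** **The 90% is never called power per stratum.** This is correct. Section 17.1 speaks of groups, defines the primary outcome as the difference between the two groups, and draws the mITT from all randomised women. A reader might infer that the protocol expressly promises 90% in each stratum; it does not. The per-stratum meaning is an inference, but a firm one: 2 x 109 = 218 is raised to 240 in each stratum and then tripled, and section 5 evaluates the primary outcome by stratum.

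**The trial is not underpowered as a whole.** Also correct. A reader might infer from the shortfall that the primary comparison is at risk. Pooled, it is not.

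**The loss alone costs little.** By the plan's own chi-square method, 15% loss lowers power to 88.2%, under two points below 90%. The rest of the drop to 85.4% comes from using Fisher's test. The two causes should be kept apart, but the test is the one the protocol names.

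**Surgical cases may stay in the analysis.** A woman who has a surgical procedure after a medical abortion can still meet every mITT condition, and nothing in the protocol excludes her. The 83% figure is therefore conditional; 102 per arm and 85% are not affected.

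**Patient records will be searched for women who miss follow-up.** This may bring missing outcomes below 15%. It does not make the statement that 240 compensates for 15% true.

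**Success does not require every stratum to be significant.** A reader might be tempted to multiply stratum powers. The protocol sets no such criterion, so a joint probability is not relevant.

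**Conclusion.** The sample-size statement is wrong as written. 240 per stratum covers 9.2% loss, while the protocol claims to cover 15% and a further 3-5%. This follows from the protocol's own figures under either inflation rule and does not depend on how surgical cases are handled.

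Under 15% loss, 80% versus 60% and a two-sided 5% level, power within a stratum is about 85% with Fisher's exact test, against an implied 90%. It is about 83% only on the added assumption that 5% surgical cases are not evaluable. The shortfall is moderate, about 5 to 7 points. It bears on conclusions within a stratum and leaves the pooled comparison unaffected, so it should be fixed but does not threaten the trial's main result.

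**What to change.** Keep 720 women. In sections 5 and 17.1:

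- Delete the claim that 240 per stratum compensates for the stated losses.
- State that, with 15% loss to follow-up, 240 per stratum leaves about 102 evaluable women per arm and gives about 85% power within a stratum for 80% versus 60% with Fisher's exact test (about 83% if 5% surgical cases are also not evaluable).
- Say explicitly that this power refers to a single stratum.
- State that the comparison pooled over strata has more than 99.9% power for the same difference.

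The cost is protocol wording only, with a less favourable power figure per stratum. Recruitment, procedures and analyses do not change.
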